### F.8 Subject accountability

Subjects may withdraw from the study at any time and for any reason, no subject replacement will be considered. Since no device is implanted nor used for diagnostic or therapeutic purposes, but will be used just to collect data, request for permission to follow-up subjects outside the clinical study in case of withdrawal due to problems related to investigational device safety or performance is not applicable in this study.

If a subject decides to withdraw from the study, the investigator will document in the Study Exit Case Report Form the reason for withdrawal and indicate any relationship of the withdrawal to the study. Subject's subsequent health care will be unaffected by withdrawal. The investigator may elect to withdraw the subject from the study at any point if deemed to be in the subject's best interest (e.g. the subject becomes too fatigued when performing walking exercises).

### F.9 Study deviations and CIP changes

A study deviation is an event where the investigator or site personnel did not conduct the clinical study according to the Clinical Investigation Plan or Clinical Investigation Agreement. The investigator is not allowed to deviate from the above mentioned documents except with prior approval and under emergency circumstances. All deviations shall be documented and explained, regardless the reason for the deviation.

Medtronic will assess the significance of all deviations and evaluate the need to amend the Clinical Investigation Plan or to early terminate the study, in accordance with Medtronic SOPs.

#### F.9.1 Request for approval of study deviations

The investigator shall obtain documented approval from Medtronic and, if required, from EC, before implementation of any change in or deviation from the Clinical Investigation Plan. The

investigator shall timely contact the Clinical Study Manager for review of the proposed change/deviation.

Prior approval is not always realistic in situations where unforeseen circumstances are beyond the investigator's control. However, also in these cases, the event is considered a deviation and shall be reported.

In any emergency situation the investigator shall exercise his/her judgment to safeguard the subject's interest. Such deviations from the Clinical Investigation Plan do not require the prior approval of Medtronic. The investigator shall report the deviation as soon as possible to Medtronic and the reviewing EC, if applicable. Medtronic will inform the regulatory authorities, if required.

#### *F.9.2 Reporting requirements for study deviations*

Study deviations will be collected throughout the study and reported to Medtronic on a Protocol Deviation Form, one for each Protocol Deviation and documenting an explanation of the deviation.

The investigator shall adhere to EC requirements and procedures for reporting study deviations.

Medtronic is responsible for analyzing deviations, assessing their significance, and identifying any additional corrective and/or preventive actions (e.g. amend the CIP, additional training, terminate the study, etc.). Repetitive or serious investigator compliance issues may represent a need to initiate a corrective action plan, and in some cases freeze enrolment or ultimately terminate the investigator's participation in the study.

#### *F.9.3 Amendments to the Clinical Investigation Plan*

The investigator will propose any appropriate modification(s) of the Clinical Investigation Plan or investigational device or investigational device use. Medtronic will review this proposal and decide whether the modification(s) will be implemented.

Medtronic will submit any significant amendment to the Clinical Investigation Plan, including a justification for this amendment, to the appropriate regulatory authorities and to the investigator to obtain approval from their EC, if applicable. Administrative amendments to the Clinical Investigation Plan will be submitted to the EC and appropriate regulatory authorities for notification, if applicable.

## **G QUALITY CONTROL PROCEDURES**

### **G. 1 Procedures for data management**

#### *G.1.1 Data collection*

The investigator must ensure accuracy, completeness, legibility and timeliness of the data reported in the Paper CRFs and in all other required reports. Data reported on the CRFs which are derived from source documents (e.g. hospital records) must be consistent with the source documents or the discrepancies need to be justified in a documented rationale, signed and dated by the (principal) investigator, to be filed in the patient medical file.

Only authorized persons can complete CRFs. CRFs shall be signed by investigators as specified on the Delegated Tasks List included in the Investigator Site File.

In order to maintain an audit trail, changes or corrections in CRFs are made by making a single strike-through on the wrong data and an addition of the correct data. The change in the CRF must be signed, dated, and explained (if necessary) by the person that made the change. If a person only authorized to complete CRFs made changes to an already signed CRF, the investigator shall re-sign this CRF.

Beside the data on the Case Report Forms, LINQ files, Accelerometer files, Holter files will be collected by means of SD cards, while CAREN system files will be collected by means of an external Hard Drive

All data shall be secured against unauthorized access. The privacy of each subject and confidentiality of his/her information shall be preserved in reports and when publishing any data.

Additional details regarding data management will be described in the Data Management Plan.

A copy of final Case Report Forms will be provided under a separate cover.

### *G.1.2 Source data to be directly recorded on the Case Report Forms*

The following data will be recorded directly on the CRF and is considered as source data:

ETGUG data, FTSTS timing, Gait speed (4MGS test), Distance covered in 6 minutes (6MW test). Refer to Table 3 for further details:

Table 3 –Source data to be directly recorded on CRFs	
Data	Source Document
LINQ placement	CRF
Holter placement and recording	CRF
Accelerometer placement and recording	CRF
ETGUG test	CRF
FTSTS test	CRF
6MW test	CRF
4MGS test	CRF
Exit subject	CRF
Study deviations	CRF

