### Devices used in the study

The following products will be worn externally by the patients to capture movement signal:

- 3-D accelerometer – ActiGraph™ wGT3X-BT
- Accelerometer - Reveal LINQ™ with software RAMware REEF Research System, Rev 1.0 onboard
- DR220 Holter

All medical devices used in this study are CE marked. The intended use of the Reveal LINQ in this study will not be for medical purposes, but exclusively for technical reasons, therefore the Reveal LINQ will be considered a non-medical device in this study. The Reveal LINQ device will be used externally, will have the investigational software RAMware REEF Research System, Rev 1.0 onboard. The software will be downloaded through the 2090 programmer. Since RAMware REEF Research System is an accessory to the Reveal LINQ it will also be classified as a non-medical device. Subjects will perform part (i.e. Six Minute Walk Test, 4 Meter Gait Speed Test) of the walking exercises inside the Computer Assisted Rehabilitation Environment (CAREN) system, to record additional subject position information.

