### *C.1.1 Primary objectives*

The primary objective of this study is to compare Gait parameters (i.e. gait speed, walking patterns) derived from the Reveal LINQ accelerometer signals during the Six Minute Walk (6MW) Test, 4 Meter Gait Speed (4MGS) Test, Five Times Sit to Stand (FTSTS) Test, Expanded Timed Get-Up-and-Go (ETGUG) Test with those obtained from a validation accelerometer and the CAREN system.

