### **F.3 Walking exercises**

No devices are implanted in this study. Before the Walking protocol is initiated the RAMware will be downloaded onto the device via the 2090 programmer.

At the beginning of the walking exercises:

- The Reveal LINQ memory will be cleared
- The Reveal LINQ, the accelerometers and the DR220 Holter monitor will be placed on the subject. A medical-grade adhesive will be placed underneath the Reveal LINQ as an additional safety measure aiming to avoid direct contact with the patient's skin
- Time will be recorded;

- The Reveal LINQ and the Actigraph will be manually tapped simultaneously to provide a marker for the further data analysis;

The following exercises will be performed:

- Six Minute Walk (6MW) Test

The 6MW test measures the distance an individual is able to walk over a total of six minutes on a flat surface. The goal is for the individual to walk as far as possible in six minutes. The 6MW test will be performed within the CAREN system environment

- 4 Meter Gait Speed (4MGS) Test

The 4MGS test measures the gait speed an individual is able to walk over 4 meters on a flat surface. The goal is for the individual to walk as fast as possible over 4 meters.

It will be repeated 3 times within the aforementioned 6MW test (after approximately 1, 3 and 5 minutes) to get variability due to subject tiredness. The test will be performed within the CAREN system environment.

- Five Times Sit to Stand (FTSTS) Test

The STS test measures the time a subject takes to stand up from an armchair 5 times in a row, without stopping in between. It is a short test which measures dynamic balance and functional mobility.

- Expanded Timed Get-Up-and-Go (ETGUG) Test

The ETGUG test measures the time it takes a subject to stand up from an armchair, walk a distance of 10 m, turn, walk back to the chair, and sit down. It is a short test of basic mobility skills for frail community-dwelling elderly.

To minimize potential bias due to subject tiredness and fatigue during the execution of the physical tests:

- The order of the tests will be randomly defined at discretion of the investigator;
- A resting time between tests may be granted, at discretion of the investigator.

The tests may or may not be conducted by the same investigator.

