# **H DATA ANALYSIS AND REPORTING**

## **H.1 Analysis of clinical data**

Descriptive statistics will be used to summarize the patient demographic and clinical characteristics at baseline. Data for qualitative variables will be presented as prevalence rates (total number of subjects, number of events, and percent). Data for continuous variables will be summarized using measures of central tendency and dispersion.

All subjects who signed the informed consent document will be defined as the All Enrolled Population. The Analysis Population is defined as subjects who are enrolled and complete at least one of the walking exercises. Subjects who are enrolled but are found to have a protocol deviation such that the clinical interpretability of the results obtained from the patient is impacted, will not be included in the primary analysis, but will be reported in the patient disposition table. The analysis exclusion of subjects due to inclusion or exclusion criteria violation or a significant CIP deviation will be decided upon by the study team blinded without prior knowledge of statistical analysis results. Safety will be reported on the All Enrolled Population and the primary objective will be reported on the Analysis Population.

During the study all movement data is continuously collected. The primary endpoint for this study are the gait parameters obtained from the Reveal LINQ – REEF Research System, Rev 1.0 (accelerometer) and the external reference system (i.e. validation accelerometer and/or computer assisted rehabilitation system). All data processing will be performed offline.

The gait speed (and additional parameters) will be calculated from the Reveal LINQ accelerometer signals, from the validation accelerometer and/or from the computer assisted rehabilitation system. Correlation coefficients between the Reveal LINQ parameters and those from the reference system will be calculated for each maneuver (4MGS, FTSTS, ETGUG and 6MHW). The agreement between the Reveal LINQ derived parameters and the reference parameters will be reported and visualized using Bland and Altman plots.

The agreement between the parameters derived during the different maneuvers will also be evaluated using correlation coefficients and Bland-Altman plots.

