The intended use of the Reveal LINQ in this study is not for medical purposes, but exclusively for technical reasons, therefore the Reveal LINQ is considered a non-medical device in this study. The Reveal LINQ device is used externally with the investigational software RAMware REEF Research System, Rev 1.0 onboard. The software is downloaded through the 2090 programmer. Since RAMware REEF Research System is an accessory to the Reveal LINQ it is also classified as a non-medical device.

Subjects perform part (i.e. Six Minute Walk Test, 4 Meter Gait Speed Test) of the walking exercises inside the Computer Assisted Rehabilitation Environment (CAREN) system, to record additional subject position information.

The Clinical Investigation Plan V. 1 17 FEB 2017 has been used to develop this Statistical Analysis Plan with the purpose to describe the Final Analysis foreseen for FRAP Study.

4. Study Objectives

The primary objective of this study is to compare Gait parameters (i.e. gait speed, walking patterns) derived from the Reveal LINQ accelerometer signals during Six Minute Walk (6MW) Test, 4 Meter Gait Speed (4MGS) Test, Five Times Sit to Stand (FTSTS) Test, Expanded Timed Get-Up-and-Go (ETGUG) Test with those obtained from a validation accelerometer and the CAREN system.

5. Investigation Plan

This is a prospective, non-randomized, single-center post-market interventional study. The Study will take place in the Netherlands at one investigation site. No randomization and no blinding will be used in this Study.

Inclusion criteria

- Chronic Heart Failure in NHYA class II and class III.
- Willing to sign the informed consent form.
- At least 18 years of age.

Exclusion criteria

- Not able to walk continuously for a period of 6 minutes and perform the walking exercises as necessary for the study protocol.
- Any known allergy to Titanium
- Any concomitant conditions which in the opinion of the investigator would not allow accurate measurement of gait and frailty parameters with an externally worn device.
- Any concomitant condition which in the opinion of the investigator would not allow a safe participation in the study.
- Enrolled in another study that could confound the results of this study, without documented pre-approval from a Medtronic study manager

6. Determination of Sample Size

The FRAP study is primarily designed to evaluate the possibility of extracting walking patterns from the accelerometer embedded in the Reveal LINQ.

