7.9. Evaluation of Objectives

No formal statistical hypothesis will be tested.

The gait speed (and additional parameters) will be calculated from the Reveal LINQ accelerometer signals, from the validation accelerometer and/or from the computer assisted rehabilitation system. Correlation coefficients between the Reveal LINQ parameters and those from the reference system will be calculated for each maneuver (4MGS, FTSTS, ETGUG and 6MHW). The agreement between the Reveal LINQ derived parameters and the reference parameters will be reported and visualized using

Bland and Altman plots. The agreement between the parameters derived during the different maneuvers will also be evaluated using correlation coefficients and Bland-Altman plots.

Additional exploratory analyses of the data will be conducted as deemed appropriate.

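### For FTSTS and ETGUG the planned reference reduces to body-worn accelerometers, and no planned analysis compares LINQ with the results recorded on the CRF

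*Protocol*

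**What the plan says.** **Objective.** Protocol C.1.1 compares LINQ gait parameters from all four tests "with those obtained from a validation accelerometer and the CAREN system". The protocol synopsis and SAP section 4 say the same.

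**Where the tests are done.** The protocol synopsis, under the devices heading, states "Subjects will perform part (i.e. Six Minute Walk Test, 4 Meter Gait Speed Test) of the walking exercises inside the Computer Assisted Rehabilitation Environment" (CAREN). SAP section 3 agrees: "Subjects perform part (i.e. Six Minute Walk Test, 4 Meter Gait Speed Test) of the walking exercises inside the Computer Assisted Rehabilitation Environment". Protocol F.3 confirms it for the six-minute walk, "The 6MW test will be performed within the CAREN system environment", and for the 4MGS, which is nested in that walk. For FTSTS and ETGUG, F.3 does not mention CAREN.

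**Planned comparison.** Protocol H.1: "Correlation coefficients between the Reveal LINQ parameters and those from the reference system will be calculated for each maneuver (4MGS, FTSTS, ETGUG and 6MHW"). Agreement is to be shown with Bland-Altman plots. SAP 7.9 gives the sources of the parameters: "The gait speed (and additional parameters) will be calculated from the Reveal LINQ accelerometer signals, from the validation accelerometer", and/or from CAREN. H.1 and SAP 7.2 define the reference system in the same two terms.

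**What the CRF holds.** Protocol G.1.2 lists as data recorded directly on the CRF: "ETGUG data, FTSTS timing, Gait speed (4MGS test), Distance covered in 6 minutes (6MW test"). Its Table 3 names the CRF as source document for all four tests. FTSTS timing and ETGUG phase data are endpoints in C.2.

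**The concern.** Detecting sit-stand phases is one of the two targets in the study aim (Protocol C.1). FTSTS and ETGUG are the two tests that involve rising from a chair, and F.3 defines both by the time taken. If CAREN does not observe them, LINQ is judged only against other accelerometers worn on the body. The designated source record of the test result, which is a named endpoint for FTSTS, enters no specified comparison.

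At stake is what a good agreement result would mean. If LINQ and ActiGraph both detect the start of a chair rise late, or its end early, they agree with each other and both misstate the test time. The planned plots could not show this. The objective also claims a CAREN comparison for two tests for which the procedures do not provide one.

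**Working it through.** The documents give no error SD, error correlation or precision target, so there is no figure of the plan's own to reproduce. The check traces each test through the documents and then shows how the choice of reference acts on a Bland-Altman analysis.

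**Step 1: trace each test.**

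| Test | In CAREN? (synopsis, F.3, SAP 3) | Result on CRF? (G.1.2) | Reference left under H.1 and SAP 7.9 |
|---|---|---|---|
| 6MW | Yes | Yes | ActiGraph and/or CAREN |
| 4MGS | Yes | Yes | ActiGraph and/or CAREN |
| FTSTS | Not listed | Yes (timing) | ActiGraph |
| ETGUG | Not listed | Yes (content not specified) | ActiGraph |

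The synopsis section on treatment describes two 3D accelerometers, one on the chest and one at the waist. Protocol B.2 puts LINQ on the left side of the chest. The between-maneuver comparison in H.1 and SAP 7.9 does not bring in CRF values either.

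**Step 2: common bias.** Let T be the true test time and b a timing bias shared by both devices. The mean LINQ-minus-ActiGraph difference is (T + b) − (T + b) = 0 for any b. Against a CRF time with its own bias c, the mean difference is b − c, so b becomes visible to the extent that c is small. This step does not depend on the error correlation.

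**Step 3: random error.** Assume that each device has error SD s = 1.0 s against T, and that the two errors correlate at ρ. Then SD of the difference = s√(2(1 − ρ)), and the limits are ±1.96 times that SD.

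| ρ | SD of difference (s) | Limits (s) |
|---|---|---|
| 0 | 1.41 | ±2.77 |
| 0.25 | 1.22 | ±2.40 |
| 0.5 | 1.00 | ±1.96 |
| 0.8 | 0.63 | ±1.24 |
| 0.9 | 0.45 | ±0.88 |

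Limits against true time would be ±1.96 × 1.0 = ±1.96 s. The device-to-device limits equal this at ρ = 0.5; they are narrower above it and wider below it.

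**Step 4: cost of a CRF reference.** Assume an independent timing error with SD 0.3 s in the CRF value. The SD of LINQ minus CRF is √(1.0² + 0.3²) = 1.044 s, with limits ±1.96 × 1.044 = ±2.05 s, compared with ±1.96 s against true time.

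**The case against.** The strongest defence is that the comparator is a declared choice. The aim defines the reference as the 3D accelerometer, CAREN, or both, and both documents say openly that only part of the exercises take place in CAREN. Protocol C.3 and C.7 describe a feasibility study of about 20 subjects with no hypothesis tested. Comparison with a reference accelerometer is a legitimate main analysis for that purpose and should stay. This keeps the point at the level of a worthwhile improvement, but it does not resolve the objective's wording or give the two tests a reference other than accelerometers.

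Several stronger readings are tempting, and the documents do not support them:

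- **That the protocol states FTSTS and ETGUG are done outside CAREN.** This is inferred from the closed list in the synopsis and SAP section 3 and from the silence of F.3. No sentence says so.
- **That the CRF times will never be used.** H.1 and SAP 7.9 allow further exploratory analyses, which would permit the comparison. They do not specify it.
- **That agreement will look too good.** For random error this needs ρ above 0.5. The documents give no ρ and describe no algorithm, only that processing is offline. The waist ActiGraph sits at a different site from LINQ, so a high ρ cannot be assumed. Nor does any document show that a shared bias exists.
- **That the CRF holds an independent stopwatch time.** The CRF is under separate cover (Protocol L.2), and the timing method is not stated in the text provided.
- **That a CRF comparison would validate the sit-stand phases.** A total time cannot check phase boundaries or stand-up slope.

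**Conclusion.** The point holds in a limited form. For FTSTS and ETGUG the planned reference reduces to body-worn ActiGraphs, the CRF-recorded results are not named as comparator in any planned analysis, and the primary objective names CAREN for tests that the procedures do not place there. Close LINQ-ActiGraph agreement would show that the devices agree. It would not show that LINQ recovers the test time, because any shared timing bias has no effect on the difference.

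The size cannot be fixed from the documents. Under the assumed 1.0 s error SD, the limits run from ±2.77 s to ±0.88 s as ρ goes from 0 to 0.9, so the plan could understate or overstate LINQ's accuracy. The conclusion rests on two things: the inference about where the two tests are done, and, for the remedy to help, a CRF time taken independently of the devices.

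**What to change.** 1. In Protocol H.1 and SAP 7.9, replace the and/or wording with the reference for each maneuver.
2. Add LINQ-derived FTSTS time against the CRF-recorded FTSTS time, by correlation and Bland-Altman plot. Do the same for ETGUG total time where the CRF records it. Make both conditional on the CRF time being taken independently of LINQ and ActiGraph, and state how it is taken.
3. Keep LINQ versus ActiGraph as a second comparison for these times, and as the comparison for ETGUG phases and stand-up slope.
4. In the primary objective (protocol synopsis, Protocol C.1.1, SAP section 4), limit CAREN to the 6MW and 4MGS.

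The cost is wording plus two more correlations and plots, from results that G.1.2 already plans to collect. Timing error in the CRF value may widen the limits slightly, and the total-time check leaves the phase boundaries unvalidated. The report should say both.

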### *G.1.3 Data review and processing*

Data management will be done according to Medtronic SOPs and the Data Management Plan for this clinical study. These documents will be made available on request.

All collected data will be reviewed for completeness, correctness and consistency. In case of issues, queries will be sent to the investigator to complete, correct or comment the data.

